- 16.3.2.5.4 Second primary tumor is defined as any different histology of sarcoma or any other type of malignancy inside or outside the radiation field.
- 16.3.2.6 Adverse Events: All eligible patients that have initiated treatment will be considered evaluable for assessing adverse event rate(s). The maximum grade for each type of adverse event will be recorded for each patient, and frequency tables will be reviewed to determine patterns. Additionally, the relationship of the adverse event(s) to the study treatment will be taken into consideration. Late toxicities (as defined in sections 16.3.2.4) will be summarized separately.
- 16.3.2.7 Quality of Life Measurements – PROMIS-10: Results from the ten-item PROMIS questionnaire will be used to evaluate physical health and mental health, separately. Changes in raw score from baseline to 24-months post-surgery will be assessed, in each of the physical and mental health domains. The Wilcoxon signed-rank test will be utilized to assess changes in raw PROMIS scores. Mean change, along with standard deviation will be reported.
- A scoring table to compare this patient population to global means may be utilized for various timepoints. However, because this scoring table is prepared for a fixed set of items, it can only be used when an examinee responds to all of the items in the set. This, along with all other analyses, including graphical representations and comparisons between other timepoints or subgroups of patients may be performed, but will be considered exploratory.
- 16.3.2.8 Quality of Life Measurements – TESS: Results from the Toronto Extremity Salvage Score (TESS) questionnaire will be used to evaluate functional outcomes. The TESS specifically measures performance of activities of daily living, and is separated into upper and lower extremity versions (29 and 30 questions, respectively).
- Patients will fill out the appropriate version, and point totals will be summed. Mean change from baseline to 24 months post-surgery, along with standard deviation will be reported by version. The Wilcoxon signed-rank test will be used to assess changes in TESS scores within questionnaires. All other analyses, including graphical representations, GEE model creation, and comparisons between different timepoints or subgroups of patients may be performed, but will be considered exploratory.

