General Guidelines 
This questionnaire is designed as a measure of physical disability for patients undergoing limb salvage surgery for musculoskeletal tumours. It is a self-administered questionnaire.
 
There is an upper extremity and lower extremity version of the questionnaire. It is recommended that study personnel complete the general information and review the instructions and sample questions with the subjects. The subjects can independently answer the remaining questions. Total completion time of the questionnaire averages 10 minutes.
 
Scoring
 
Each question is a measure of the difficulty that the individual has performing the task. The total potential score for an item is a perfect performance score (ie. 5).
 
The scale has been designed to allow individuals to respond to a non-applicable category on an item if it is not something they perform in their everyday life. Consequently, a total questionnaire score, if desired, would be a standardized score ranging from 0 to 100 calculated by:
 $\frac{\text{sum of the item scores} - \# \text{ items}}{\text{possible score range}} \times 100\%,$ 
where, sum of the item scores = sum of difficulty responses # items = items completed excluding the NA response items possible score range = $(5 \times \# \text{ items}) - (1 \times \# \text{ items})$
 
Mail Administration
 
The TESS questionnaires have been administered by mail and, although formal testing of measurement properties has not been undertaken, patients are able and willing to complete the forms and the scores fall within anticipated ranges.
		

SS	RTOG Study 0630	Case #	
PLACE LABEL HERE			
Institution Participant's Initials	Institution No. Participant's I.D. No.		
Toronto Extremity Salvage Score (Davis, 1996)			
Upper Extremity Questionnaire Lower Extremity Questionnaire			
Completed by patient at baseline, 12, 18, and 24 months from the start of treatment.			
Note: only the upper or lower extremity form is completed, not both			
TESS - UPPER EXTREMITY			
Patient Study ID#: _____	Patient Initials: _____ (first/middle/last)		
Date of birth: _____ (day/month/year)	Form Completion Date: _____ (day/month/year)		
Months from start of treatment	 Baseline  12 months  18 months  24 months		

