Months from start of treatment 
  Baseline  12 months  18 months  24 months 			
Site: 
  1 Bone  2 Soft Tissue 			

The following questions are about activities commonly performed in daily life. Each question asks that you mark each item (as in the examples below) opposite the description that best describes your ability to perform each task during the past week. Some activities will be extremely easy for you to do, others will be extremely difficult or impossible.
			
EXAMPLE Riding a bicycle is: 
  impossible to do.  extremely difficult.  moderately difficult.  a little bit difficult.  not at all difficult. 			
888  This task is not applicable for me.			

You should choose the response "impossible to do...." if the activity is something that you normally do in your daily activities but are now unable to do because of physical limitations such as weakness, stiffness or pain.
			

If you do not perform an activity as part of your normal lifestyle you would choose the response "888" to indicate that the item is not applicable.
			

Mark all items ensuring that you choose the description that most accurately describes your abilities in the past week.
			

SS	RTOG Study 0830	Case #
PLACE LABEL HERE		
Institution	Institution No.	
Participant's Initials	Participant's I.D. No.	

The following questions ask about your ability to perform activities that are common to everyday life. Considering the amount of difficulty you have performing the activity due to the current problem you are having with your leg, please answer the questions by choosing the answer that best describes your ability to do the activity over the past week.

1) Putting on a pair of pants is:

1. impossible to do.
2. extremely difficult.
3. moderately difficult.
4. a little bit difficult.
5. not at all difficult.

888 This task is not applicable for me.

2) Putting on shoes is:

1. impossible to do.
2. extremely difficult.
3. moderately difficult.
4. a little bit difficult.
5. not at all difficult.

888 This task is not applicable for me.

3) Putting on socks or stockings is:

1. impossible to do.

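### TESS is to be analysed as a raw sum of points, although Appendix III scores it 0–100 over applicable items only; the raw change can have the wrong size or sign

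*Combined protocol and SAP*

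**What the plan says.** Section 16.3.2.8 gives one scoring instruction for the TESS: "Patients will fill out the appropriate version, and point totals will be summed". The two planned analyses use that total: "Mean change from baseline to 24 months post-surgery, along with standard deviation will be reported by version", and "The Wilcoxon signed-rank test will be used to assess changes in TESS scores within questionnaires". The upper and lower extremity forms have 29 and 30 activity items. The section does not mention not-applicable answers, code 888 or the scoring formula.

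The scoring notes in Appendix III start from the not-applicable option: "The scale has been designed to allow individuals to respond to a non-applicable category on an item". As a consequence, they say, "a total questionnaire score, if desired, would be a standardized score ranging from 0 to 100". The formula subtracts the number of items from the sum of item scores, divides by the possible score range (5 × items − 1 × items) and multiplies by 100. The number of items is defined as "items completed excluding the NA response items".

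Both forms print 888 under every numbered activity item. Their instructions reserve it for activities outside the patient's ordinary life: "If you do not perform an activity as part of your normal lifestyle you would choose the response" 888. An activity the patient would normally do but has lost through weakness, stiffness or pain is to be scored 1, the lowest category.

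**The concern.** Read as written, 16.3.2.8 uses a different total from the one the instrument defines in the same document. If 888 is simply left out of the sum, a not-applicable item contributes 0 points. That is below the 1 point for an activity the patient cannot do at all. An item that stops being relevant to a patient's life then looks like a loss of function larger than total inability.

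The TESS is the instrument 16.3.2.8 names for functional outcome, and it serves secondary objective 2.2.6. The mean change, its standard deviation and the signed-rank test would all combine two things: how well patients perform, and how many items they counted as applicable. Two analysts could also score the same data differently, one summing and the other standardising.

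**Working it through.** **Inputs from the documents.** Items per form: 29 upper, 30 lower (16.3.2.8). Item scores: 1 to 5, or 888 for not applicable (Appendix III forms). Score = (S − n)/(5n − n) × 100, where S is the sum over the n applicable items (Appendix III).

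**Assumed.** The item scores and not-applicable counts below are illustrations; the documents give none.

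**1. The stated 0–100 range.** All items at 1: S = n, score 0. All items at 5: S = 5n, score (5n − n)/(4n) × 100 = 100. The range holds for any n. The raw sum instead runs from n to 5n: 30 to 150 with 30 items, 25 to 125 with 25.

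**2. What each measure tracks.** Let m be the mean score over applicable items, so S = n·m.
- Appendix III score = (n·m − n)/(4n) × 100 = 25(m − 1). It depends on m only.
- Raw change = n₂m₂ − n₁m₁ = n₂(m₂ − m₁) + m₁(n₂ − n₁). The first term is change in function; the second is change in the number of applicable items.

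**3. Illustrative patients.**

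| Case | Raw total | Appendix III score |
|---|---|---|
| A. 30 items at 4; 3 become NA, 27 stay at 4 | 120 → 108 (−12) | 75.0 → 75.0 (0) |
| B. 30 items at 4; 5 become NA, 25 stay at 4 | 120 → 100 (−20) | 75.0 → 75.0 (0) |
| C. 30 items at 4; 13 rise to 5, 12 stay at 4, 5 become NA | 120 → 113 (−7) | 75.0 → 88.0 (+13.0) |
| D. 25 items, mean 4.4; then 30 items, mean 4.0 | 110 → 120 (+10) | 85.0 → 75.0 (−10.0) |
| E. Upper form: 29 items, mean 4.0; then 25 items, mean 4.4 | 116 → 110 (−6) | 75.0 → 85.0 (+10.0) |
| F. 30 items at both visits, all rise from 3 to 4 | 90 → 120 (+30) | 50.0 → 75.0 (+25.0) |
| G. 25 items at both visits, all rise from 3 to 4 | 75 → 100 (+25) | 50.0 → 75.0 (+25.0) |

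Case C in full: 13 × 5 + 12 × 4 = 113 and (113 − 25)/100 × 100 = 88.0. By step 2, m₂ = 113/25 = 4.52, so the raw change is 25 × 0.52 + 4 × (−5) = 13 − 20 = −7.

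A and B show a wrong size; C, D and E show a wrong sign. F and G show that with a stable not-applicable set the sign is right, but the same per-item gain still counts differently according to n.

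More generally, with 30 items all at one score between 3 and 5 and 1 to 5 of them becoming not applicable, the raw change is between −3 (1 × 3) and −25 (5 × 5). The Appendix III change is 0.

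**4. Not applicable against unable.** Three items falling from 4 to 1 give 27 × 4 + 3 × 1 = 111, a loss of 9. The same three becoming not applicable give 27 × 4 = 108, a loss of 12.

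**5. How much improvement a raw sum can hide.** If k of 30 items become not applicable, the raw sum falls unless m₂ exceeds 30m₁/(30 − k). In Appendix III points that is a gain of 25·m₁·k/(30 − k). At m₁ = 4 and k = 1, 2, 3 or 5, the gain must exceed 3.4, 7.1, 11.1 or 20.0 points.

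**6. What standardising does not remove.** With 27 items at 4 and 3 at 2, S = 114 and the score is (114 − 30)/120 × 100 = 70.0. If those three become not applicable, it is (108 − 27)/108 × 100 = 75.0, although no remaining item changed. Scored on the 27 common items, the change is 75.0 − 75.0 = 0.0.

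**The case against.** The strongest reply is that 16.3.2.8 never calls the TESS total raw, whereas the PROMIS-10 paragraph just before it uses that word twice. Summing is the first step of the Appendix III formula, and the appendix is part of the same protocol. On that reading only a cross-reference is missing. The reading is possible, but 16.3.2.8 does not say so: it states a sum, stops, and analyses the result. The appendix makes a total optional, yet once a total is used it offers only the standardised one. The PROMIS-10 paragraph also warns that its scoring table requires an answer to every item, so the plan recognises dependence on a fixed item set there but not for the TESS.

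Second, the forms reserve 888 for activities outside normal life, so the not-applicable set should reflect lifestyle rather than treatment and may be fairly stable. This stands as a limit: a wrong sign needs the number of applicable items to differ between visits. Work, driving and sport items could change over two years, but nothing shows how often.

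Third, the examples concern single patients, and changes in both directions might partly cancel in a group mean. This also stands. The examples show how the distortion arises; they do not estimate its effect on the reported result.

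Fourth, applicable-item counts and a common-item analysis go beyond Appendix III. That is true. They address the limitation in step 6, are small extra work, and are separate from the core correction.

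**Conclusion.** The concern holds. As written, the scoring rule in 16.3.2.8 conflicts with the instrument's own rule in Appendix III, and the TESS paragraph should be corrected before analysis. In the illustrations, a raw sum can show a loss of 20 points where the Appendix III score is unchanged, or a loss of 7 where it rises by 13.0. With a stable not-applicable set, the sign is right but equal per-item gains receive unequal weight (+30 against +25).

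These sizes rest on assumed answers, and they assume that 888 is omitted from the sum. If the code were added as a number, one such item with 29 others at 4 would total 888 + 116 = 1004. The size in this trial cannot be computed from the documents. The affected outcome is secondary and descriptive; the primary endpoint, the decision rule and the sample size of 108 are unaffected.

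**What to change.** In 16.3.2.8, replace the summing instruction with the Appendix III standardised 0–100 score. State that 888 means not applicable and is excluded from both the sum and the item count. Analyse the change in that score by version, keeping the planned mean, standard deviation and signed-rank test. State also how unanswered items are treated.

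Because standardising leaves some dependence on which items apply, report the number of applicable items at each visit. Add a sensitivity analysis scored only on items applicable at both baseline and 24 months.

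The cost is SAP wording and a little programming. The forms already collect the item-level answers, including 888, so no new data are needed.

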16.4 Data Safety and Monitoring

16.4.1 Safety Review: The principal investigator(s) and the study statistician will review the study monthly to identify accrual, adverse event, and any endpoint problems that might be developing. The Mayo Clinic Cancer Center (MCCC) Data Safety Monitoring Board (DSMB) is responsible for reviewing accrual and safety data for this trial at least biannually, based on reports provided by the MCCC Statistical Office.

16.4.2 Adverse Event Stopping Rules: The stopping rule specified below is based on the knowledge available at study development. We note that the Adverse Event Stopping Rule may be adjusted in the event of either (1) the study re-opening to accrual or (2) at any time during the conduct of the trial and in consideration of newly acquired information regarding the adverse event profile of the treatment(s) under investigation. The study team may choose to suspend accrual because of unexpected adverse event profiles that have not crossed the specified rule below.

Accrual may be temporarily suspended to this study if at any time we observe events considered at least possibly related to Radiation Therapy (i.e., an adverse event with attribute specified as “possible”, “probable”, or “definite”) that satisfy one of the following:

- If 8 or more of the first 20 patients (or 40% or more of all patients after 10 are accrued) experience a Grade 3+ AE.
- If 4 or more experience a Grade 5 AE at any time.

After consideration by the study team (Study Chair, statistician, etc.), a decision will be made as to whether accrual can be resumed. In addition, we will review grade 4 and 5 adverse events deemed “unrelated” or “unlikely to be related”, to verify their attribution and to monitor the emergence of a previously unrecognized treatment-related adverse event.

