10.2 Recording Adverse Events

CTCAE term (AE description) and grade: The descriptions and grading scales found in the revised NCI Common Terminology Criteria for Adverse Events

(CTCAE) version 5.0 will be utilized for AE reporting unless as otherwise stated in the table below.

All appropriate treatment areas should have access to a copy of the CTCAE version 5.0. A copy of the CTCAE version 5.0 can be downloaded from the CTEP web site:

(http://ctep.cancer.gov/protocolDevelopment/electronic_applications/ctc.htm)

10.2.1 Adverse event monitoring and reporting is a routine part of every clinical trial. First, identify and grade the severity of the event using the CTCAE version 5.0. Next, determine whether the event is expected or unexpected and if the adverse event is related to the medical treatment or procedure. With this information, determine whether the event must be reported as an expedited report (see Section 10.3).

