10.2.2 Assessment of Attribution

Only G4 or G5 adverse events will require an attribution. Any change in the grade of an adverse event within the list of monitored AEs will be recorded and considered to be related to treatment. Any new adverse not listed occurring within the radiated area or in close proximity will be graded and attribution defined by the study PI.

Events determined to be possibly, probably or definitely attributed to a medical treatment suggest there is evidence to indicate a causal relationship between the treatment and the adverse event.

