10.3 Reporting of Serious Adverse Events and Unanticipated Problems

When an adverse event has been identified, the study team will take appropriated action necessary to protect the study participant and then complete the Study Adverse Event Worksheet and log. The sponsor-investigator will evaluate the event and determine the necessary follow-up and reporting required.

- a. Serious Adverse Events will be reported as part of regular adverse event reporting mechanisms via the data capture system and logged for review reporting.

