10.3.1 Investigator Reporting: Notifying the Mayo IRB

The IRB requirements reflect the guidance documents released by the Office of Human Research Protections (OHRP), and the Food and Drug Administration (FDA) in early 2007 and are respectively entitled “Guidance on Reviewing and Reporting Unanticipated Problems Involving Risks to Subjects or Others and Adverse Events” and “Guidance for Clinical Investigators, Sponsors, and IRBs: Adverse Event Reporting – Improving Human Subject Protection.”

- 10.3.1.1 According to Mayo IRB Policy any serious adverse event (SAE) which the Principal Investigator has determined to be a UPIRTSO must be reported to the Mayo IRB as soon

- 10.3.1.2 as possible but no later than 5 working days after the investigator first learns of the problem/event.
Non-UPIRTSO – the investigator reports problems or events that do NOT meet criteria of an UPIRTSO in summary format at the time of the next continuing review. The investigator monitors the severity and frequency of subsequent non-UPIRTSOs.

Consider the following information to collect when developing any forms for documentation of adverse events.

Example

Information collected on the adverse event worksheet (and entered in the research database):

- Subject's name:
- Medical record number:
- Disease/histology (if applicable):
- The date the adverse event occurred:
- Description of the adverse event:
- Relationship of the adverse event to the research (drug, procedure, or intervention):
- If the adverse event was expected:
- The severity of the adverse event: (use a table to define severity scale 1-5)
- If any intervention was necessary:
- Resolution: (was the incident resolved spontaneously, or after discontinuing treatment)
- Date of Resolution:

The investigator will review all adverse event reports to determine if specific reports need to be made to the IRB and FDA. The investigator will sign and date the adverse event report when it is reviewed. For this protocol, only directly related SAEs/UPIRTSOs will be reported to the IRB.

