- 10.4 Solicited toxicities to be graded at each evaluation and pretreatment symptoms/conditions to be evaluated based on the schedule of events using the CTCAE v5.0 grading unless otherwise stated in the table below. This regimen has established safety, based on this article [https://www.thelancet.com/journals/lanonc/article/PIIS1470-2045\(22\)00638-6/fulltext](https://www.thelancet.com/journals/lanonc/article/PIIS1470-2045(22)00638-6/fulltext) so the focus is on solicited toxicities and not any adverse event after radiation therapy is completed.

ACUTE TOXICITIES – Upper Proximal Extremity			
CTCAE System/Organ/Class (SOC)	Adverse Event / Symptoms	Baseline	During RT & Preoperative Assessment

General disorders and administration site conditions	Fatigue	X	X
Skin and subcutaneous tissue disorders	Dermatitis Radiation	X	X
	Hyperpigmentation	X	X
Neoplasm benign, malignant and unspecified	Tumor pain	X	X

LATE TOXICITIES – Upper Proximal Extremity		
CTCAE System/Organ/Class (SOC)	Adverse Event / Symptoms	Post-Surgery & Follow Up
Skin and subcutaneous tissue disorders	Hyperpigmentation ¹	X
Vascular	Lymphedema ²	X
General disorders and administration site conditions	Localized edema ¹	X
Musculoskeletal and connective tissue disorders	Fibrosis deep connective tissue ¹	X
	Joint range of motion decreased ²	X
	Osteonecrosis ¹	X

Neoplasm benign, malignant and unspecified	Tumor pain ¹	X
Injury, poisoning and procedural complications	Fracture ¹	X
Gastrointestinal Disorders ¹	Esophageal fistula	X
Respiratory, thoracic and mediastinal disorders	Pneumonitis ¹	X

¹ Specific to radiation / surgery treatment area

² Specific to ipsilateral extremity / region

ACUTE TOXICITIES – Upper Distal Extremity (includes elbow)			
CTCAE System/Organ/Class (SOC)	Adverse Event / Symptoms	Baseline	During RT & Preoperative Assessment
General disorders and administration site conditions	Fatigue	X	X
Skin and subcutaneous tissue disorders	Dermatitis Radiation	X	X
	Hyperpigmentation	X	X
Neoplasm benign, malignant and unspecified	Tumor pain	X	X

LATE TOXICITIES – Upper Distal Extremity (includes elbow)		
CTCAE System/Organ/Class (SOC)	Adverse Event / Symptoms	Post-Surgery & Follow Up
Skin and subcutaneous tissue disorders	Hyperpigmentation ¹	X
Vascular	Lymphedema ²	X
General disorders and administration site conditions	Localized edema ¹	X
Musculoskeletal and connective tissue disorders	Fibrosis deep connective tissue ¹	X
	Joint range of motion decreased ²	X
	Osteonecrosis ¹	X

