10.5 Submit via appropriate *reporting mechanisms* the following AEs experienced by a patient through the course of Radiation Therapy and not specified in Section 10.4:

10.5.1 Grade 3, 4, and 5 AEs regardless of attribution to the study treatment or procedure.

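### Should section 16.4.2 say whether primary-endpoint wound complications count towards its adverse-event stopping rule?

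*Combined protocol and SAP*

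**What the plan says.** Section 16.4.2 allows a temporary suspension of accrual when events at least possibly related to RT satisfy either of two limbs. The first is "If 8 or more of the first 20 patients (or 40% or more of all patients after 10 are accrued) experience a Grade 3+ AE". The second is four or more Grade 5 events. The rule applies throughout the study and may be adjusted as information accrues. The team may also suspend without a crossing, and after a crossing it decides whether accrual resumes. The primary endpoint is not mentioned and no operating characteristics are given.

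Other sections bear on whether a wound complication is counted.

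- **Section 10.2.1** asks staff to "identify and grade the severity of the event using the CTCAE version 5.0" and then to judge expectedness and relatedness.
- **Section 10.2.2** opens with "Only G4 or G5 adverse events will require an attribution". Its next sentence treats any grade change in a monitored event as treatment-related. The one after covers new unlisted events "occurring within the radiated area or in close proximity will be graded and attribution defined by the study PI".
- **Section 10.3** tells the team to "complete the Study Adverse Event Worksheet and log". The example worksheet in 10.3.1 includes severity and relationship to the research.
- **Section 10.4** lists solicited toxicities without wound complications, and explains the choice: "so the focus is on solicited toxicities and not any adverse event after radiation therapy is completed".
- **Section 10.5** requires submission of Grade 3 to 5 events "experienced by a patient through the course of Radiation Therapy and not specified in Section 10.4".
- **Appendix VI**, the wound form, has no grade or attribution field. Appendices IV and V have both.

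On the denominator, 16.4.2 refers to patients accrued, and 16.3.2.6 takes eligible patients who have started treatment as evaluable for adverse events. Section 16.4.1 adds a monthly review by the investigators and statistician, which covers endpoint problems, and DSMB review at least twice a year.

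**The concern.** Wound complication is the main hazard under study. Section 16.2 plans for 35% and calls 45% or above inferior, so a 40% boundary falls between the two. At 35%, seven of the first 20 patients are expected to have an event (20 × 0.35 = 7), against a trigger of eight.

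If every wound complication counts, an acceptable regimen could often meet the rule. If none counts, the Grade 3+ limb does not respond to the trial's own safety endpoint. Sections 10.4 and 10.5 and Appendix VI point towards not counting; sections 10.2.1, 10.2.2 and 10.3 point towards counting. Two careful teams could therefore run different rules from the same text. At stake would be either needless interruptions of accrual or a high wound complication rate with only discretionary review to catch it.

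**Working it through.** **1. The plan's own figure (16.2, 16.2.2, 16.2.4).** One-sided alpha 0.10, power 0.80, P0 = 0.45, P1 = 0.35:

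N = [(1.2816 × √(0.45 × 0.55) + 0.8416 × √(0.35 × 0.65)) / 0.10]² = 107.95, so 108.

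Normal-approximation power at 108 is 80.01%, as stated, and 108 / 0.90 = 120. The design reproduces. The stopping rule has no stated figure to reproduce.

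**2. Inputs for the rule.** True rates of 35% and 45% are from 16.2, and 4 patients a month is from 16.2.3. The share s of wound complications that are Grade 3+ and at least possibly RT-related is not given; I take 60%, 80% and 100% as an assumed range. The per-patient probability is p = s × true rate. All results cover wound complications only.

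**3. First-20 clause, exact.** P(Bin(20, p) ≥ 8):

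| Share | True 35% | True 45% |
|---|---|---|
| 60% | p = 0.21: 4.2% | p = 0.27: 14.5% |
| 80% | p = 0.28: 17.1% | p = 0.36: 43.6% |
| 100% | p = 0.35: 39.9% | p = 0.45: 74.8% |

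**4. The 40% clause with immediate outcomes.** Exact recursion for the probability that count/n ever reaches 0.40, up to n = 120, at a true 35%:

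| Checks | 60% | 80% | 100% |
|---|---|---|---|
| Every patient from 10 | 17.2% | 40.6% | 71.6% |
| Every patient from 11 | 12.1% | 34.6% | 68.0% |
| Every 4 patients from 12 | 10.5% | 31.0% | 64.3% |

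**5. Either clause with delayed outcomes.** Simulation, 40,000 runs: 4 patients a month, 30 monthly reviews, 40% clause from patient 11. Assumed timings are RT start 7 days after registration, surgery 42-49 days after RT start, and events spread over 0-120, 10-60 or 14-45 days after surgery.

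| True rate, denominator | 60% | 80% | 100% |
|---|---|---|---|
| 35%, treatment started | 4% | 17% | 41-42% |
| 35%, completed 120 days | 8% | 27-28% | 61% |
| 45%, treatment started | 15% | 45-47% | 83-87% |
| 45%, completed 120 days | 24% | 66% | 96% |

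Using all accrued patients changes the treatment-started figures by no more than about one point. If 10% of patients yield no event but stay in the denominator (the loss allowed for in 16.2.2), the 35% results become 2%/5%, 11%/18% and 28%/43% (treatment started / completed) for shares of 60%, 80% and 100%.

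**6. Other events.** The rule counts every qualifying Grade 3+ event. Adding an assumed independent 5% or 10% rate of other qualifying events raises the 35% results on the accrued denominator from 4% to 10% or 19%, from 17% to 29% or 42%, and from 40% to 55% or 71%. None of the tables above is therefore an upper limit for the rule as a whole.

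**7. Reading the text.** The opening sentence of 10.2.2 sets a minimum, not a ban on attributing lower grades: Appendices IV and V ask for attribution at every grade. The second sentence gives listed events a default attribution. The third gives the investigator the task for unlisted events in or near the irradiated tissue, and a complication of the irradiated surgical bed fits that description. Section 10.4 states a focus and 10.5 governs submission during RT; neither removes an event from 16.4.2. What remains without a required attribution is a Grade 3 unlisted event away from the treated area.

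**The case for a change.** The strongest case for a change is that the main safety endpoint of the trial should not depend on inference across sections. At a true 35%, the chance of meeting the limb from wound complications runs from about 4% to 72% depending on unstated choices, and it is nil if they are excluded. A sentence in 16.4.2 and two fields on Appendix VI would cost little.

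Part of this stands. The text does not say that endpoint events count, the maturity of the denominator is open, and no operating characteristics are reported.

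The rest is weaker. Grade 3 events do not generally lack an attribution once all of 10.2.2 is read. Excluding wound complications would not remove every numerical limit, since a fatal RT-related one would still enter the Grade 5 limb. The denominator is largely given as accrued or treated patients, so the completed-120-day results describe a reading the section does not state.

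Adding a separate numerical flag is a trade-off rather than a correction. With a uniform prior and looks at 20, 40, 60 and 80 assessed patients, flagging when the posterior probability of a rate above 45% exceeds 0.95 triggers 0.7% of the time at a true 35% but only 11% at 45%. Lowering the threshold to 0.80 gives 6.3% and 40%.

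**Conclusion.** No change is called for. The silence in 16.4.2 is real, but it is missing detail that the team can fill sensibly. The investigator grades and attributes wound complications in the irradiated bed under 10.2.2, and the monthly review reads the tally knowing that some patients are still inside the 120-day window.

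The size is about 4-17%, 17-41% and 40-72% for meeting the Grade 3+ limb at a true 35%, for shares of 60%, 80% and 100%. The low ends come from the first-20 clause or from delayed events over all treated patients; the high ends from immediate outcomes checked at every patient from the tenth. The shares and timings are assumptions, and other Grade 3+ events would raise the figures.

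These are chances of meeting a rule that permits a temporary pause, not chances of closing the trial. The team may resume accrual, adjust the rule or suspend without it, and endpoint and safety problems are already under monthly and DSMB review. The rule plays no part in the primary Z-test on 108 patients, so the primary result stays sound if the plan is followed as written.
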